- k Serum chemistry will include the following: aspartate aminotransferase (AST); alanine aminotransferase (ALT); total, direct, and indirect bilirubin levels; alkaline phosphatase (ALP); albumin; creatinine; urea; total protein; sodium; chloride; calcium; phosphate; potassium; and glucose (random). Creatine phosphokinase (CPK) and estimated glomerular filtration rate (eGFR) is to be performed at Screening only. eGFR will be calculated using the Bedside Schwartz Equation in pediatric participants (10 to < 18 years old) and using the Cockcroft and Gault method in adult participants.
- l Hematology will include the following: hemoglobin, hematocrit, erythrocyte count (red blood cell [RBC] count), thrombocyte count (platelets), mean platelet volume, leukocyte count (white blood cell [WBC] count) with differential in absolute counts (including neutrophils, eosinophils, basophils, lymphocytes, and monocytes). Local laboratories will be used for platelet analysis required at ALL visits (ie, Clinic Visits and Weekly Lab Visits in between Clinic Visits).
The central laboratory will be used for the analyses required at Clinic Visits including hematology, differential, and reticulocytes. The results of hematology, differential and reticulocytes obtained at local laboratories will be used only if the central lab results of Clinic Visits are missing due to any reason. Central platelet counts assessed at Clinic Visits will be used if local platelet results are missing for any reason.
- m Coagulation will include: PT/INR, thrombin time, activated partial thromboplastin time (aPTT), and fibrinogen level.
- n Hemolysis panel: consisting of Coombs test, haptoglobin levels.
- o PK samples for participants aged 18 years or older will be collected predose (within 1.5 hours predose) and 2 hours postdose (± 15 minutes) at the Week 1 visit. PK samples for pediatric participants (see [Appendix 10.7](#) for EU [EEA countries] age ranges) will be taken Predose (within 1.5 hours predose) and postdose at the following timepoints: 0.5 hours (± 5 mins), 2 hours (± 5 mins) and 4 hours (± 15 mins), 6 hours (± 15 mins) at the Week 1 visit. At the Week 13 visit a sample will be taken Predose only. At these visits, participants will wait to take their morning dose until they complete the blood draw of pre-dose sample.

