- u* This visit is for platelet count assessment and can be conducted on-site or remotely. After the end of treatment (EOT) visit, weekly platelet count assessment is not required; however, it is up to the Investigator to decide whether to conduct weekly platelet assessments using unscheduled visits, if deemed necessary for participant safety.
- v* SARS-CoV-2 molecular test (if COVID-19 testing is required per local guidelines to be determined for each site).
- w* During the blinded treatment period (Week 13 to Week 24): Participants who discontinue from the blinded treatment period due to safety (or other) reasons and choose to join the open label period will attend the Week 25 assessments at their next scheduled visit.
- x* **All participants who discontinue treatment during the blinded or open-label period need to have an Early Termination visit as specified in Table 1 and an End of Study visit (4 weeks after last IMP intake) as specified in the End of Study visit in Table 2 (See End of Study [Table 2](#)).**

Table 2 - Schedule of Assessments - Open Label Period

	Open Label Period								End of Study 4 weeks post-last dose SD393	Weekly Lab Visits Between Clinic Visits ^r	Early Termination/ Unscheduled visit
	First Day of WK25 ^{a, p} SD169	WK 29 SD197	WK33 SD225	WK37 SD253	WK41 SD281	WK45 SD309	WK49 SD337	First Day of WK53 ^q SD365			
Visit Window	±3 days	±3 days	±3 days	±3 days	±3 days	±3 days	±3 days	±3 days	±3 days	±3 days	
AEs	X	X	X	X	X	X	X	X	X		X
Concomitant Medications	X	X	X	X	X	X	X	X	X		X
Height (cm) ^a	X			X				X			
Weight (kg)	X	X	X	X	X	X	X	X	X		X
Physical exam ^b	X	X	X	X	X	X	X	X	X		X
ECG (12-lead, single)	X ^c							X	X		X
Vital Signs	X	X	X	X	X	X	X	X	X		X
Urinalysis ^d	X	X	X	X	X	X	X	X	X		X
Pregnancy test ^e	X	X	X	X	X	X	X	X	X		X
Serum Chemistry ^f	X	X	X	X	X	X	X	X	X		X
Hematology, differential, reticulocytes ^g	X	X	X	X	X	X	X	X	X	X ^r	X
T/B/NK counts ^m	X	X	X		X			X	X		
PT/INR, aPTT ^h	X	X	X	X	X	X	X	X	X		
TPO levels ^m	X	X	X	X	X	X	X	X	X		
Hemolysis panel ^{i, m}	X	X	X	X	X	X	X	X	X		
Immunoglobulin Levels ^m	X	X	X		X			X	X		
PK sample ⁱ	X							X			X
BTK Occupancy (at select sites) ^{k, m}	X							X			
(Optional) sample for vaccine-specific IgG ^{m, n}	←=====→										X
QOL Questionnaires ^l	X	X	X	X	X	X	X	X	X		X
IBLS	X	X	X	X	X	X	X	X	X		X
Rilzabrutinib dispensed	X	X	X	X	X	X	X	X			
Patient Medication Diary	X	X	X	X	X	X	X	X			
SARS-CoV-2 test (see Appendix 10 for country-specific requirements)	X										

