- r This visit is for platelet count assessment and can be conducted on-site or remotely. Lab visits will occur weekly from Week 25 to Week 53. The Investigator can request that the participant visits the clinic for additional platelet monitoring during unscheduled visits if needed. After the end of treatment (EOT) visit, weekly platelet count assessment is not required; however, it is up to the Investigator to decide whether to conduct weekly platelet assessments using unscheduled visits, if deemed necessary for participant safety.

Table 3 - Schedule of Assessments - Long-Term Extension

	On-treatment clinic visits				Early Termination/ Unscheduled Visit
	Week 53/Rollover to LTE ⁿ	Clinic Visits Every 28 Days for the first year of LTE then every 3 months thereafter	Last Day of Active Rilzabrutinib Treatment	End of Study (4 weeks post-last dose)	
Visit Windows	±7 days	±7 days	±7 days	±7 days	
AEs	X	X	X	X	X
Concomitant Medications ^a	X	X	X	X	X
Weight (kg)	X	X	X	X	X
Physical Exam ^b	X	X	X	X	X ^m
ECG (12-lead, single)	X			X	X ^m
Vital Signs	X	X	X	X	X
Urinalysis ^c	X	X	X	X	X
Pregnancy test ^d	X	X	X	X	X
Serum Chemistry ^e	X	X	X	X	X
Hematology, differential, reticulocytes ^f	X	X	X	X	X
T/B/NK counts ^{g, k}	X	X		X	
PT/INR aPTT ^h	X	X	X	X	
TPO levels ^k	X	X	X	X	
Hemolysis panel ^{i, k}				X	
Immunoglobulin Levels ^k				X	
(Optional) sample for vaccine-specific IgG ^{k, l}	←=====→				X
QOL Questionnaires ^j	X	X	X	X	X
IBLS	X	X	X	X	X
Rilzabrutinib dispensed	X	X			
Patient Medication Diary	X	X			X ^m
SARS-CoV-2 test (see Appendix 10 for country-specific requirements)	X				X ^m

AE = adverse event; aPTT = activated partial thromboplastin time; CS = corticosteroids; ECG = electrocardiogram; EQ-5D-5L = EuroQOL-5 Dimension 5 Level; IBLS = ITP Bleeding Scale; IgG = immunoglobulin G; INR = international normalized level; ITP = Immune thrombocytopenia; ITP-PAQ = ITP-Patient Assessment Questionnaire; ITP-KIT = Kids' ITP Tools; PGIS = Patient Global Impression of Severity PGIS-Fatigue = Patient Global Impression of [Fatigue] Severity; QOL = Quality of Life; SD = study day; T/B/NK = T-lymphocytes/B-lymphocytes/natural killers; PGIC = Patient Global Impression of Change; PT = prothrombin time; TPO = Thrombopoietin; TPO- RA = thrombopoietin receptor agonist

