## 5.4 APPENDIX 4 DATA HANDLING CONVENTIONS

### Analysis windows for time points

The following analysis windows will decide how the scheduled and/or unscheduled visits will be used in the by-visit analyses of efficacy, safety, vital sign, ECG, IBLS, QOL variables.

Platelet counts conducted locally will be used for efficacy analyses. Platelet counts conducted centrally will be used as a back-up for missed or non-analyzable local lab samples.

A scheduled measurement will be used if it is available. Otherwise, an unscheduled measurement will be allocated to a scheduled visit if it is within the analysis window of the scheduled visit.

After applying these time windows, if multiple assessments are associated to the same time point, the closest from the targeted study day will be used. If the difference is a tie, the value after the targeted study day will be used. If multiple valid values exist within a same day, then the first value of the day will be selected.

If there is no measurement for a given parameter in an analysis window, data will be considered missing for the corresponding visit.

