**Table 12 - Analysis window definition for unscheduled measurements**

Scheduled Visit	Targeted study day (Analysis window) for Platelet Count a	Targeted study day (Analysis window) for Others b
Week n c	1+7*(n-1) (+/-3)	-
Week 5	29 (+/-3)	29 (-13, +14)
Week 9	57 (+/-3)	57 (-13, +14)
Week 13	85 (+/-3)	85 (-13, +14)
Week 17	113 (+/-3)	113 (-13, +14)
Week 21	141 (+/-3)	141 (-13, +14)
Week 25	169 (+/-3)	169 (-13, +14)
Week 29	197 (+/-3)	197 (-13, +14)
Week 33	225 (+/-3)	225 (-13, +14)
Week 37	253 (+/-3)	253 (-13, +14)
Week 41	281 (+/-3)	281 (-13, +14)
Week 45	309 (+/-3)	309 (-13, +14)
Week 49	337 (+/-3)	337 (-13, +14)
Week 53	365 (-3, +14)	365 (-13, +14)
Month 1 LTE	393 (-13, +14)	393 (-13, +14)
Month 2 LTE	421 (-13, +14)	421 (-13, +14)
Month 3 LTE	449 (-13, +14)	449 (-13, +14)

Scheduled Visit	Targeted study day (Analysis window) for Platelet Count a	Targeted study day (Analysis window) for Others b
Month 4 LTE	477 (-13, +14)	477 (-13, +14)
Month 5 LTE	505 (-13, +14)	505 (-13, +14)
Month 6 LTE	533 (-13, +14)	533 (-13, +14)
Month 7 LTE	561 (-13, +14)	561 (-13, +14)
Month 8 LTE	589 (-13, +14)	589 (-13, +14)
Month 9 LTE	617 (-13, +14)	617 (-13, +14)
Month 10 LTE	645 (-13, +14)	645 (-13, +14)
Month 11 LTE	673 (-13, +14)	673 (-13, +14)
Month 12 LTE	701 (-13, +42)	701 (-13, +42)
QX_LTE where X=1,2,3,....	701+28*3*X for X=1,2,3,.... (-41, +42)	

Study days are calculated considering Day 1 as the day of first administration of intervention (or the day of randomization for participant not exposed).

a Applicable to hematology, differential, reticulocytes. Hematology are measured weekly up to protocol Week 53, then every 4 weeks for 1 year, then quarterly afterwards.

b Applicable to parameters other than hematology, differential, reticulocytes.

c n = 2-4, 6-8, 10-12, 14-16, 18-20, 22-24, 26-28, 30-32, 34-36, 38-40, 42-44, 46-48, 50-52.

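### SAP Table 12 gives all hematology the weekly platelet windows, although the protocol measures only platelets weekly; low materiality, limited to by-visit hematology summaries up to Week 53

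*Protocol*

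**What the plan says.** **Protocol.** The schedules for the blinded and open-label periods (Tables 1 and 2) mark the row for hematology, differential and reticulocytes under the weekly laboratory visits. The mark carries a footnote that narrows it. Table 1, footnote u: "This visit is for platelet count assessment and can be conducted on-site or remotely". Table 2, footnote r, describes the visit in the same way and adds "Lab visits will occur weekly from Week 25 to Week 53". Table 1, footnote l, assigns platelets to local laboratories at every visit, then says of the rest: "The central laboratory will be used for the analyses required at Clinic Visits including hematology, differential, and reticulocytes". Table 2, footnote g, matches it. Clinic visits are 4 weeks apart.

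**SAP section 5.4, Table 12.** Column 2 is headed for platelet count. It gives every week from 2 to 52 a window of 3 days either side of target, and Week 53 a window from 3 days before to 14 days after. Footnote a widens the column's scope: "Applicable to hematology, differential, reticulocytes. Hematology are measured weekly up to protocol Week 53, then every 4 weeks for 1 year, then quarterly afterwards". Column 3 runs from 13 days before to 14 days after each 4-weekly clinic visit. Footnote b closes it to hematology: "Applicable to parameters other than hematology, differential, reticulocytes".

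**SAP rules that limit the effect.** Section 5.4: "A scheduled measurement will be used if it is available"; an unscheduled value is considered only otherwise. Section 3.6.3.1 bases the by-visit laboratory statistics on central values in the on-treatment period, and the PCSA analyses on all measurements, local or central, scheduled or not. The unscheduled-visits paragraph of section 5.4 also uses unscheduled values for baseline, last on-treatment value and shift summaries.

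**The concern.** Footnote a contradicts the protocol schedule and the heading of its own column. Hemoglobin, neutrophils and the other non-platelet counts are 4-weekly tests, yet they are windowed as weekly ones. Chemistry, taken at the same clinic visits, gets a 28-day window (13 + 1 + 14), and hematology gets 7 days.

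Change from baseline in hematology is a stated safety endpoint, and the protocol lists cytopenia as a class effect of BTK inhibitors. The list of statistical changes in SAP Table 11 records that central hematology samples were subject to clotting, so missing central values are a practical possibility. The protocol would fall back on local hematology when the central result is missing, but the central-only rule in SAP section 3.6.3.1 does not allow that in the by-visit statistics. An unscheduled central draw is then the only substitute, and the narrow window restricts it.

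**Working it through.** **1. Reproduce the table.** The target day is 1 + 7 × (n − 1). For Weeks 5, 9, 13, 17, 21 and 25 this gives Days 29, 57, 85, 113, 141 and 169, and for Week 53 it gives Day 365, all as printed. Weeks 2 to 53 comprise 13 clinic weeks and 39 weeks without a clinic visit.

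**2. Column 2, blinded period.** The windows for Weeks 2 to 25 run from Day 5 (8 − 3) to Day 172 (169 + 3), which is 24 × 7 = 168 days.
- Clinic weeks: 6 × 7 = 42 days; 42/168 = 25%.
- Weeks with no full hematology scheduled: 18 × 7 = 126 days; 126/168 = 75%.

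**3. Column 3, same days.** The first window opens on Day 16 (29 − 13), and the windows then run without a gap. Days 16 to 172 are 157 days; 157/168 = 93%. Days 5 to 15 (11 days) precede the first window, so moving hematology to column 3 would re-map 126 − 11 = 115 days to a clinic visit.

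**4. Up to Week 53.** Days 5 to 379 (365 + 14) are 375 days. Weeks without a clinic visit cover 39 × 7 = 273 days; 273/375 = 72.8%. Column 3 would re-map 273 − 11 = 262 of them. From Month 1 to Month 12 of the long-term extension the two columns are identical, so the mismatch ends at Week 53.

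**5. One draw.** The target for Week 6 is 1 + 7 × 5 = Day 36. Neutrophils from an unscheduled central draw on Day 36 go to Week 6. The Week 5 window in column 3 is Days 16 to 43, so ALT from the same draw could serve Week 5, but only if the scheduled Week 5 ALT is missing too.

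**6. When a clinic-visit row changes.** All of the following must hold:
- the scheduled central value is missing;
- an on-treatment unscheduled or early-termination central sample exists;
- that sample lies more than 3 days from target (for Week 53, more than 3 days before or 14 days after).

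**7. Scale, on assumptions only.** Let m be the chance that the clinic value is missing for a participant with an unscheduled central draw, and suppose that draws are spread evenly over Days 5 to 172. The share of unscheduled central values that the fix would bring into a clinic-visit row is 115/168 × m = 0.685 × m. For m = 2%, 5%, 10% and 20% this is 1.4%, 3.4%, 6.8% and 13.7%. The documents supply neither m nor the timing of draws.

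**The case against.** A reader might infer that most unscheduled hematology values are dropped from the safety summaries because of this window. The documents do not support that, for four reasons.

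- If the clinic-visit value exists, the scheduled-first rule keeps a repeat out of that row under either column. A repeat prompted by an abnormal result is in this group, so the window makes no difference to it.
- Local results are excluded from the by-visit statistics by the central-only rule, whatever the window.
- The 25% and 93% count calendar days. Protocol section 9.3.8.1 asks for repeats of unexplained clinically significant values within 72 hours of reporting, so draws need not be evenly spread and some may fall inside the narrow window.
- The values are not lost. The PCSA analyses, baseline, last on-treatment value and shift summaries still use unscheduled values, and neutropenia and anemia are analyzed separately as adverse events of interest.

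Nor do the documents say that a table row will be printed for a week without scheduled hematology. Section 3.6.3.1 speaks of scheduled visits. Section 5.4 allocates values to such weeks, but the output is left open.

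The SAP wording also has a source: the schedule row is marked under the weekly visits, and only the footnote narrows it. Finally, 3 days is the protocol's own visit window, and a wider one lets a Day 43 value stand for Day 29. It would also place platelets and hemoglobin from one blood count at different visits.

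All of this stands as a limit on the effect. It does not make footnote a correct. Platelets and the other counts follow different schedules, and the SAP already accepts the 28-day window for every other 4-weekly laboratory parameter.

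**Conclusion.** Footnote a of SAP Table 12 is wrong as written for every hematology analyte except platelets, and the materiality is low. The effect is confined to descriptive by-visit hematology summaries and plots up to Week 53. First, where the scheduled central value is missing, an off-target central sample cannot fill the clinic visit, although another laboratory parameter missing at that visit could be filled from it. Second, unscheduled central values in the intervening weeks are assigned to weeks with no full hematology scheduled; these weeks hold 75% of the days from Day 5 to Day 172.

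The 75% follows from the windows alone. Turning it into a share of values needs a missing rate and a timing pattern that the documents do not give. The stronger inference, that a cytopenia signal could be hidden, is not supported, because the PCSA analyses use all measurements. No platelet efficacy endpoint is touched, since platelets really are measured weekly.

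**What to change.** In SAP Table 12, up to Week 53:
- restrict column 2 and footnote a to platelet count;
- move other hematology, differential and reticulocytes to column 3 and amend footnote b to match;
- delete the statement that hematology is measured weekly;
- say that coagulation belongs in column 3, because section 3.6.3.1 lists it under hematology.

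The long-term extension windows can stay as they are. The cost is a SAP wording change and one programming specification, with no change to data collection or to type I error. The small downside is that a value up to 14 days from target may stand for a clinic visit, as the SAP already allows for other laboratory parameters.

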2. BACKGROUND

2.1. Overview of Immune Thrombocytopenia (ITP)

Immune Thrombocytopenia (ITP) is characterized by autoantibody-mediated destruction of platelets and impaired platelet production, which result in thrombocytopenia and a predisposition to bleeding associated with morbidity and mortality.

In general, pharmacotherapy (corticosteroids [CSs], intravenous immunoglobulin [IVIg] or anti-D) is used for symptomatic participants with low platelet counts for reducing platelet destruction. While a majority of participants respond initially to CSs, the rate of continued remission is low. Second line therapies include rituximab and splenectomy and are associated with risk of sepsis and immune suppression. Thrombopoietin (TPO) mimetics ([Bussel 2007](#)) are approved for the treatment of participants with chronic ITP who have not had sufficient responses to CSs, IVIg, or splenectomy. Second-line treatment with TPO-RAs have a clinical response rate of 80%, however approximately one-third of participants discontinue TPO-RAs due to lack of response ([Ghanima 2019](#)). Novel, safe, and effective oral treatments to maintain platelet counts in this setting would be a significant therapeutic advantage. Thus, there remains a high unmet medical need for novel, safe, and effective oral therapies for ITP.

2.2. BTK Inhibitor Rilzabrutinib

Bruton's Tyrosine Kinase (BTK) is expressed in cells of the B-cell lineage, including marrow-derived hematopoietic stem cells, common lymphoid progenitor cells and developing B and myeloid lineages. BTK is also expressed in other cells of hematopoietic lineage with the exception of T cells, natural killer cells and plasma cells ([Sideras 1995](#), [Rip 2018](#)).

A BTK inhibitor such as rilzabrutinib has the potential to target multiple pathways and cell types involved in inflammation and autoimmunity. These include B-cell receptor-mediated B-cell pathways, FcγR-induced cytokine release from monocytes and macrophages, FcεR-induced mast cell degranulation and granulocyte migration and mediator release.

There is preliminary evidence to support the role of BTK inhibition in participants with autoimmune cytopenias ([Rogers 2016](#), [Montillo 2017](#)), where sequential episodes of severe autoimmune hemolytic anemia and ITP ceased after initiation of treatment with ibrutinib, a BTK/epidermal growth factor receptor /interleukin-2-inducible T-cell kinase inhibitor, in participants with chronic lymphatic leukemia (CLL).

Rilzabrutinib is a high-affinity inhibitor of BTK. Pertinent to the treatment of ITP, rilzabrutinib treatment in vitro profoundly inhibited human B-cell activation and blocked antibody (IgG, IgE) mediated activation of immune cells via Fc receptor signaling.

2.3. Nonclinical Experience

The nonclinical safety profile of rilzabrutinib has been well-characterized in safety pharmacology studies and repeat-dose oral toxicity studies in multiple animal species. Orally administered rilzabrutinib did not affect the gross behavioral, physiological, or neurological state of rats at dose levels up to 500 mg/kg/day and the no-observed-adverse-effect level (NOAEL) of the cardiovascular and respiratory systems in dogs considered to be 500 mg/kg/day.

Rilzabrutinib was well-tolerated in rats and dog studies of up to 6- and 9-month duration, respectively. In 6-month oral rat study, the NOAEL for female rats was 50 mg/kg/day (area under the plasma concentration curve [AUClast] 5480 hr.ng/mL) and 150 mg/kg/day in males (AUClast 5327 hr.ng/mL), based on lethality, decreased body weight gain, macroscopic and microscopic changes in the gastrointestinal (GI) tract, and neutrophilic inflammation in the brain. In a 9-month oral dog study, the NOAEL was 30 mg/kg/day (AUClast 963 hr.ng/mL), based on body weight loss and the euthanasia of 1 male dog at 50 mg/kg/day. The estimated human exposure of 400 mg twice daily (BID) at steady state is 890 hr.mg/mL. Rilzabrutinib was not genotoxic and did not demonstrate toxicities in fertility and early embryo-fetal development reproductive studies. Overall, the nonclinical safety profile of rilzabrutinib supports continuation of clinical studies. Additional nonclinical information on rilzabrutinib is provided in the current version of the rilzabrutinib (PRN1008) [Investigator's Brochure](#) (IB).

Please refer to the IB for more details.

2.4. Clinical Experience

As of the data cut-off date of 22 April 2021, Rilzabrutinib was administered to 289 healthy volunteers and was well-tolerated.

Details of clinical experience with rilzabrutinib in the PRN1008-005 (NCT02704429) study in participants with pemphigus and PRN1008-010 study in participants with ITP can be found in the IB. Preliminary efficacy results of PRN1008-010 Part A of the study were presented at European Hematology Association 2020 ([Kuter 2020](#)).

2.4.1. Safety

As of the data cut-off date of 22 April 2021, in 8 completed Phase 1 studies and 4 ongoing Phase 1 studies (more than 280 healthy volunteers), the completed Phase 2 study in participants with pemphigus (41 participants, PRN1008-005), and ongoing Phase 1/2 studies in ITP (61 participants, PRN1008-010), and IgG4 (4 participants, PRN1008-017), rilzabrutinib demonstrated a safety profile characterized by predominantly mild-to-moderate adverse events (AEs) such as GI disturbance and headache, no rilzabrutinib-related deaths, and no evidence of increased risk of infections. There have been no related thrombotic or major bleeding events in the clinical experience with rilzabrutinib to date. In addition, there are no patterns or clinically significant findings from physical examinations, laboratory parameters, electrocardiograms (ECG), or vital signs in healthy-volunteers and in participants from studies conducted to date.

The most common treatment-related AEs as of 22 April 2021 were GI in nature, including nausea, vomiting, and diarrhea. The majority of treatment-emergent adverse events (TEAEs) were mild to moderate in severity. There was 1 serious adverse event (SAE) in Study PRN1008-005 that was assessed by the Sponsor as related to the study drug (cellulitis). Safety and efficacy findings of Study PRN1008-010 (main treatment periods) and LTE-Part A interim analysis were published ([Kuter et al 2022](#), [Cooper et al 2023](#), [Kuter et al 2024](#)). Please refer to the most recent version of the IB for updated safety information.

The marketed BTK inhibitor, ibrutinib, has been studied in combination with rituximab in the treatment of chronic lymphocytic leukemia without published evidence of increased drug-related

AEs ([Burger 2019](#)). There is no a priori drug interaction potential between anti-CD20 biologic drugs and the small molecule rilzabrutinib.

PRN1008-010 (Part A and Part B) study results demonstrated a rapid and sustained platelet response in patients with primary ITP who failed multiple prior therapies and showed a favorable safety profile (Kuter et al 2022, Cooper et al 2023). For summary of overall benefit/risk assessment, refer to [Section 2.7](#).

